#### 4.3 Data Integrity

A proprietary signal quality index (SQI) will be used to confirm the quality of the signals during recording as well as during post-processing analysis. This SQI will be used to prospectively remove sections of data that may result in poor performance due to motion artifacts or other noise contaminations.

### 5.0 Eligibility/Subject Enrollment

#### 5.1 Inclusion Criteria

- Adults aged 18 years or older,
- Willing and able to provide informed consent,
- Able to comply with study procedure.

#### 5.2 Exclusion Criteria

- Any member defined under ‘Special Population’ in the AAMI standards (Pregnant, children, arm circumference > 42 cm),
- Patient with a pacemaker,
- History of reactions to medical adhesives,
- Inability to comply with the study procedure,
- Non-English Speaker.

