#### **3.1 Study Design**

This is a prospective study designed to validate the PHP by comparing its BP measurements with those from an FDA-cleared ambulatory BP cuff (Norav NBP One). The study will include 85 participants who will undergo a series of BP measurements over a 20-minute period while simultaneously wearing the PHP and ambulatory BP (ABP) cuff. This study will be conducted in home and office environments, including patients' homes and the offices of Perin Health Devices ([name]). An initial BP measurement will be taken, followed by four reference BP measurements and three paired test device measurements.

The study will also include an optional cold pressor test to further evaluate the device's performance on intra-patient variability. The cold stimulus activates afferent sensory pathways that, in turn, trigger a sympathetic response resulting in an increase in BP. If a subject elects to participate in the cold pressor test, the validation measurements will be repeated after placing their hand in ice water for one minute.

According to AAMI standards, this study design will ensure the mean absolute error (MAE) between the PHP and the reference device does not exceed 5 mmHg with a standard deviation (SD) of  $\leq 8$  mmHg for both SBP and DBP.

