### 3.2 Study Type

This study is a Prospective Review: the data do not currently exist and will be collected over the course of this study to conduct the validation.

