## 4.0 Data/Specimen Analysis

### 4.1 Data Analysis Plan

Blood pressure from the PHP will be calculated using a proprietary algorithmic approach. The steps include:

1. Preprocessing: Areas of high motion, as determined by the accelerometer measurement are excluded from the analysis. For ECG and PPG signals, artifacts such as baseline wandering and respiratory components at lower frequencies, as well as power line harmonics and electromyogram artifacts at higher frequencies are removed. Auscultation signals are filtered to remove lung sound components and concentrate on heart sound components.
2. Segmentation: Fiducials for the ECG, PPG, and auscultation signals are extracted using respective techniques.
3. Depth-Resolved PPG: The time difference between the capillary component (blue LED) and the arteriolar component (red/IR LED) is used to calculate arteriolar PTT and SVR.
4. Feature Extraction: A combination of hand-crafted features and learned feature embeddings are extracted and concatenated into a single feature vector.
5. Deep Learning Estimation: An LSTM-based model is used to estimate SBP and DBP from the calibration value and the input feature vector.

The mean error and standard deviation of the SBP and DBP measurements from the PHP relative to the ambulatory blood pressure cuff will be calculated. Statistical analysis will include paired t-tests and Bland-Altman plots to assess the agreement between the two devices.

The feature extraction and estimation analysis will be conducted by PI [name], blinded to reference values to maintain data analysis integrity, pursuant of the company's conflict of interest policies. The evaluation and statistical comparisons against the ABP cuff will be conducted by Co-I [name] with independent validation by [name], an independent reviewer. The criteria for validation will follow AAMI standards, where the mean difference must be  $\leq 5$  mmHg and the standard deviation  $\leq 8$  mmHg.

---

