### 6.0 Consent Process & HIPAA Authorization

#### 6.1 Consent Process

Participants will be identified through self-selection via an online form shared broadly across social media, email, and web. The online form will include: (1) a description of the study (2) overview of the risks and benefits (3) contact information form. See Appendix E for the online form overview. For participants who elect to participate, they will be contacted by the study team to schedule a time to conduct the study. If the participant is not able to be contacted by phone, a follow-up email will be sent.

The consent process will take place in a private setting before any study procedures are performed. Participants will be informed, in English, about the study's purpose, procedures, risks, and benefits, and will be given the opportunity to ask questions.

Participants will be made aware that there will be no negative impacts if they refuse to participate. Consent will be obtained by either PI [name] or Co-I [name] from participants engaging in the study. The participant will be provided with a physical copy of the informed consent documentation and asked to provide a signature. The consent form will be scanned and stored securely in an electronic format for the study team. The

physical copy will be returned to the participant. The study procedure may occur immediately after receiving consent.

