### **7.0 Confidentiality**

#### 7.1 Confidentiality

Patient contact information will be stored securely. Digital copies will be encrypted, and access controlled. No physical copies of the information will be allowed. All digital copies of patient contact information will be permanently deleted at the end of the study.

Data will be coded and de-identified at the time of collection to protect participant privacy. No link logs to the above identifying information will be created or retained. Raw data files will be retained securely electronically by randomized ID for future secondary analysis. Physical artifacts (completed intake forms) will be stored securely and separately for three years and then destroyed. Data will not be shared with third parties for any reason other than for formal auditing purposes.

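### Eligibility does not exclude people whose data built the algorithm, or a second enrolment, and affected records could not be removed afterwards

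*Combined protocol and SAP*

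**What the plan says.** Section 5.1 has three inclusion criteria: "Adults aged 18 years or older", consent, and ability to comply. Section 5.2 has five exclusions: AAMI special populations, a pacemaker, past reactions to medical adhesives, "Inability to comply with the study procedure", and not speaking English. Section 5.3 repeats the age rule. None of these concerns earlier contribution of data to the algorithm or earlier enrolment in this study.

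Section 4.1 describes learned feature embeddings and then the estimator: "An LSTM-based model is used to estimate SBP and DBP from the calibration value and the input feature vector". It names no training population, model version or date at which the model is fixed, and it does not say that participants are independent of development.

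Recruitment is by "self-selection via an online form shared broadly across social media, email, and web" (Section 6.1). Visits may take place in homes or at "the offices of Perin Health Devices" (Section 3.1).

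On identity, Section 7.1 says "No link logs to the above identifying information will be created or retained" and has contact details deleted at the end of the study. Section 3.8 keeps the random ID off the consent form and discards the pre-enrollment information when the study ends. Sections 3.4, 3.5 and 6.1 have the signed consent forms scanned and stored, with no stated deletion date.

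**The concern.** A learned model has to be validated in people it was not fitted to. If some participants supplied development data, the model may carry information specific to them, and its errors in those people would tend to be smaller than in new users. The acceptance rule in Section 4.1 includes an SD limit of 8 mmHg, so such overlap pushes towards a pass. Blinding the estimation step to this study's reference values does not help, because the information would already be in the fitted weights.

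A second enrolment is a different problem. It breaks independence between records and leaves fewer than 85 distinct people, but it does not make the model look more accurate.

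The design also makes later repair difficult. If overlap were discovered after the study, the affected readings could not be picked out for a sensitivity analysis.

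**Working it through.** **1. Does any other section supply the missing rule?**

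- Section 3.2 says "the data do not currently exist and will be collected over the course of this study to conduct the validation". This makes the recordings new, not the people.
- Section 3.7 says that no existing database is accessed. This does not stop a former development volunteer from enrolling.
- The blinding and conflict-of-interest wording in Section 4.1 covers the estimation analysis, not who is enrolled.
- The questions on the pre-enrollment and intake forms are not visible in the text available, so a relevant question cannot be ruled out. Without a criterion in Section 5.2, however, a yes answer would exclude nobody.

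No section supplies the rule.

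**2. Can overlap be found and repaired later?**

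Names survive on the scanned consent forms. Duplicates could therefore be found by name, and so could development contributors if the sponsor holds their identities. With no link log and no random ID on the consent form, a name cannot be tied to a set of readings. Detection is possible; removal of the affected records is not reliable.

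**3. How much overlap would matter?**

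The plan's own figures are N = 85 (Section 4.2) and the SD limit of 8 mmHg (Section 4.1). Section 4.2 gives no difference or planning SD, so the 85 cannot be rebuilt from stated inputs; nothing below depends on how it was derived.

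The rest is assumed, because the documents give no such values:

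- S is the error SD in people the model has not seen.
- d is the error SD in people it has seen, taken as 4 to 6 mmHg.
- Mean errors are equal in the two groups.

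If a fraction f of participants has been seen, the pooled variance is (1 − f)S² + f·d². Setting this to 8² = 64 gives the smallest fraction that reaches the limit:

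f = (S² − 64) / (S² − d²), and the number of people is 85f, rounded up.

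- S = 8.3, d = 4: 4.89 / 52.89 = 0.092, which is 7.9, so 8 people.
- S = 8.3, d = 6: 4.89 / 32.89 = 0.149, which is 12.6, so 13 people.
- S = 9, d = 4: 17 / 65 = 0.262, which is 22.2, so 23 people.
- S = 9, d = 6: 17 / 45 = 0.378, which is 32.1, so 33 people.

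| SD in unseen people (mmHg) | Seen people needed of 85, d = 4 | d = 6 |
|---|---|---|
| 8.3 | 8 | 13 |
| 8.6 | 15 | 23 |
| 9 | 23 | 33 |
| 10 | 37 | 48 |

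The result is sensitive to d. At S = 8.3 and d = 7, f = 4.89 / 19.89 = 0.246, so 21 people are needed.

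**4. Do duplicates favour a pass?**

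Take one normally distributed error per person. The chance that the sample SD is at most 8 is P(χ² with n − 1 df ≤ (n − 1)·64 / σ²). Suppose five duplicates leave 85 − 5 = 80 distinct people.

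- True SD σ = 8.3: 33.7% with 85 people, 34.3% with 80.
- True SD σ = 7.7: 71.0% with 85 people, 70.5% with 80.

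The change is about half a percentage point, and its direction depends on which side of 8 the true SD lies. In general, k repeat entries leave 85 − k distinct people.

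**The case against.** The strongest reply is that nothing in the documents shows any overlap. They do not say whose data trained the model and mention no earlier volunteers. The form is circulated widely, and visits also take place in homes. Only two investigators take consent, so a returning participant might well be recognised. Each participant also has a calibration reading on the day that feeds the model, which plausibly reduces any advantage from earlier exposure. Finally, the illustration is most striking for SDs just above the limit, and a device with a true SD of 8.3 would pass the SD limit about one time in three by sampling alone (33.7% above).

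All of this stands as a limit on size and likelihood. It does not supply the missing rule: recognition by an investigator is not a criterion, and calibration does not make a participant independent of the training data.

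Three stronger readings should be resisted.

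- A reader might infer from the absence of link logs that overlap could never be traced. The stored consent scans contradict this; what is lost is the link from a name to its readings.
- A reader might treat sponsor staff and repeat enrollees as people the model has already seen. Staff are in that position only if they supplied development data, and repeat enrollees only if the model were retrained on study data, which no section proposes.
- A reader might suppose that duplicates also help the device pass. Step 4 shows that they do not do so systematically.

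**Conclusion.** The gap is real and worth closing. The eligibility rule admits people who contributed to development of a learned algorithm and people already enrolled, and no other section prevents either. Overlap with development contributors would bias the error SD downward. Under the assumed SDs this could turn a borderline fail into a pass, with 8 to 13 of 85 people at a true SD of 8.3 mmHg. It would take 23 to 33 at 9 and 37 to 48 at 10, so only extensive overlap would rescue a clearly inaccurate device.

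These counts rest on assumed SDs and equal mean errors. They are not an estimate of what will happen. Because affected readings could not be identified afterwards, the safeguard has to operate before or at enrolment.

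**What to change.** Add two exclusions to Section 5.2: anyone, including sponsor staff, who contributed data to development, training or tuning of the PHP algorithm; and anyone already enrolled in this study.

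Ask about both on the pre-enrollment or intake form. Before each visit, while contact details still exist, check the name against the enrolled list and against any list of development contributors that the sponsor holds. Record only a yes/no flag against the random ID, which respects the rule against link logs.

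The planned 85 does not change. The cost is the loss of a few easily reached volunteers and a short name check per booking. The documents do not show that a list of development contributors exists; if there is none, the participant's own answer is the only check on that criterion.

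Excluding staff who gave no development data is a separate conflict-of-interest choice and is not needed to prevent leakage.

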#### 5.3 Age Range

Adults aged 18 years or older.

### 6.0 Consent Process & HIPAA Authorization

#### 6.1 Consent Process

Participants will be identified through self-selection via an online form shared broadly across social media, email, and web. The online form will include: (1) a description of the study (2) overview of the risks and benefits (3) contact information form. See Appendix E for the online form overview. For participants who elect to participate, they will be contacted by the study team to schedule a time to conduct the study. If the participant is not able to be contacted by phone, a follow-up email will be sent.

The consent process will take place in a private setting before any study procedures are performed. Participants will be informed, in English, about the study's purpose, procedures, risks, and benefits, and will be given the opportunity to ask questions.

Participants will be made aware that there will be no negative impacts if they refuse to participate. Consent will be obtained by either PI [name] or Co-I [name] from participants engaging in the study. The participant will be provided with a physical copy of the informed consent documentation and asked to provide a signature. The consent form will be scanned and stored securely in an electronic format for the study team. The

physical copy will be returned to the participant. The study procedure may occur immediately after receiving consent.

#### 6.2 Waiver or Alteration of Consent Process

N/A (no waiver or alteration of consent process requested).

#### 6.3 HIPAA Authorization and Waivers

N/A (No HIPAA Authorization and Waiver is requested as no data are associated with or derived from a healthcare service event, data are not entered into medical records, and no PHI is collected or stored).

### **7.0 Confidentiality**

#### 7.1 Confidentiality

Patient contact information will be stored securely. Digital copies will be encrypted, and access controlled. No physical copies of the information will be allowed. All digital copies of patient contact information will be permanently deleted at the end of the study.

Data will be coded and de-identified at the time of collection to protect participant privacy. No link logs to the above identifying information will be created or retained. Raw data files will be retained securely electronically by randomized ID for future secondary analysis. Physical artifacts (completed intake forms) will be stored securely and separately for three years and then destroyed. Data will not be shared with third parties for any reason other than for formal auditing purposes.

#### 7.2 Data Security

Ensuring data security throughout the study is crucial. Data security measures include:

- Encryption: All data will be encrypted during storage and transmission using strong encryption protocols (e.g., AES-256).
- Access Control: Restricted access to the data to authorized personnel only. Implement multi-factor authentication and role-based access controls for digital data. Physical artifacts will be stored securely in a locked filing cabinet in a private office.
- Regular Audits: Conduct regular security audits to ensure that data protection measures are effective and up to date.
- Training: Provide data security training for all personnel involved in the study to ensure they understand and adhere to data protection protocols. Authorized personnel will be required to complete data handling training prior to receiving authorization of access.

### **8.0 Risks and Benefits:**

#### 8.1 Risks

Risks associated with the study include potential discomfort from BP measurements and the cold pressor test. Additional risks are associated with the adhesive from the PHP, including discomfort when placing or removing the adhesive or an adverse reaction to the

---

adhesive. There is also a risk of breach of confidentiality, which will be mitigated through secure data handling practices.

The PHP device is not FDA approved. However, we have determined that the device does not introduce any significant risk to the participant and therefore does not require an IDE (i.e., the device is IDE Exempt). See Appendix D for the IDE Exemption justification.

## 8.2 Benefits

Participants may not receive direct benefits from the study, but the findings could contribute to the development of improved BP monitoring technologies, benefiting society and the field of medical research.

## **10.0 Appendices**

- Appendix A- Consent Form
- Appendix B- Participant Intake Form
- Appendix C- Device Survey
- Appendix D- IDE Exemption Letter

---

**Appendix C- Device Survey****PATIENT ID:** \_\_\_\_\_

Please rate your level of agreement with the following statements:

**1. I found that the patch was noticeable when wearing it.**

Totally disagree     Disagree     Neutral     Agree     Totally agree

**2. I found the patch irritating on my skin.**

Totally disagree     Disagree     Neutral     Agree     Totally agree

**3. I found that wearing the patch was painful.**

Totally disagree     Disagree     Neutral     Agree     Totally agree

**4. I prefer the patch to the blood pressure cuff for monitoring my blood pressure.**

Totally disagree     Disagree     Neutral     Agree     Totally agree

**5. I would wear the patch continuously for one month to help manage my care.**

Totally disagree     Disagree     Neutral     Agree     Totally agree

---

## Appendix D- IDE Exemption Letter

### Study Title: Validation of Cuffless Blood Pressure Measurements Using the Perin Health Patch

#### Study Devices: Perin Health Patch

##### Sponsor Justification of Non-Significant Risk Device:

The Perin Health Patch in conjunction with its labeling, device classification and indications for use, does NOT meet any of the four criteria set out by the FDA to define a significant risk device. For these reasons, the Perin Health Patch is considered a non-significant risk (NSR) device and is therefore exempt from Investigational Device submissions and FDA oversight.

*Definition of a Significant Risk (SR) device under 21 CFR Part 812.3.:*

The study device(s) as listed above:

- Is not intended as an implant which would thereby present potential for serious risk to the health, safety, or welfare of a subject;
- Is not purported or represented to be for use in supporting or sustaining human life which would thereby present potential for serious risk to the health, safety, or welfare of a subject;
- Is not used for use of substantial importance in diagnosing, curing, mitigating, or treating disease, or otherwise preventing impairment of human health which would thereby present potential for serious risk to the health, safety, or welfare of a subject; and
- Does not otherwise present potential for serious risk to the health, safety, or welfare of a subject.

##### Non-Significant Risk (NSR)

- Non-Significant Risk devices are investigational devices that do not pose a significant risk to the human subjects and do not meet the definition of a SR device.

Sponsors of studies involving non-significant risk devices are not required to submit an IDE application to the FDA for approval. Submissions for non-significant device investigations are made directly to the IRB of each participating institution. The FDA considers an investigation of a non-significant risk device to have an approved IDE when the IRB concurs with the non-significant risk determination and approves the study.

The sponsor must comply with the abbreviated IDE requirements under 21 CFR 812.2(b):

- Labeling - The device must be labeled in accordance with the labeling provisions of the IDE regulations (812.5) and must bear the statement "CAUTION - Investigational Device. Limited by Federal (or United States) law to investigational use."
- IRB Approval – The sponsor must obtain and maintain Investigational Review Board (IRB) approval throughout the investigation as a non-significant risk device study (812.2 (b)).

---

- Informed Consent – The sponsor must assure that investigators obtain and document informed consent from each subject according to 21 CFR 50, Protection of Human Subjects, unless documentation is waived by an IRB in accordance with 56.109(c).
- Monitoring - All investigations must be properly monitored to protect the human subjects and assure compliance with approved protocols (812.46).
- Records and Reports - Sponsors are required to maintain specific records (812.140(b) (4) and (5) and make certain reports as required by the IDE regulations 812.150(b) (1), (2), (3), (5), (6), (7), (8), (9) and (10).
- Investigator Records and Reports – The sponsor must assure that participating investigators maintain records (812.140(a)(3)(i) and make reports as required (812.150(a) (1), (2), (5) and (7); and
- Prohibitions –Commercialization, promotion, test marketing, misrepresentation of an investigational device, and prolongation of the study are prohibited (812.7).

The Perin Health Patch thus has No Major Risks Anticipated.

The Perin Health Patch is a chest-worn device measuring 65 x 35 mm. The device records several vital signs, including skin temperature, electrocardiogram (ECG), pulse oximetry, and heart and lung auscultation. The device is powered from a lithium manganese oxide battery for 16 days of continuous use in a home environment. The electronics module is adhered to the chest with a certified long-term wear adhesive for up to 28 days of wear time.

Perin Health believes it has adequately mitigated anticipated risks through the process outlined in ISO 14971, a nine-part standard which first establishes a framework for risk analysis, evaluation, control, and review for medical devices.

Please feel free to reach out with any further questions regarding the Perin Health Patch or the IDE Exemption and Study Risk Determination.

[name].

Chief Technology Officer

Perin Health Devices

[contact]

